Title: A phase two randomized, double-blinded, placebo-controlled study combining physiological, radiographic, and biological biomarkers to study the anti-fibrotic effect of pirfenidone in CLAD post lung-transplantation

PI: [name]., M.S.

ID: HUM00131610

NCT: NCT03473340

IRB Approval Date: 5/11/2019

CLINICAL TRIAL PROTOCOL

Title:	A phase two randomized, double-blinded, placebo-controlled study combining physiological, radiographic, and biological biomarkers to study the anti-fibrotic effect of pirfenidone in CLAD post lung-transplantation		
Brief Title:	Role of pirfenidone in treatmen	t of lung transplant rejection	
Clinical Phase:	II		
Coordinating Investigator	[name]., M.S.		
	Division of Pulmonary and Critical Care Medicine, Department		
	of Internal Medicine		
	University of Michigan Health System		
	[name]		
	[name]		
	[name]		
Status:	Final		
Version and Date:	Version: 2.0 Date: January 31, 2019		

CLINICAL TRIAL PROTOCOL SYNOPSIS

Name of company	Genentech		
Name of finished product:	pirfenidone		
Name of active ingredient	pirfenidone		
Protocol date:	January 31, 2019		
Title of Trial:	A phase two randomized, double-blinded, placebo-controlled		
	study combining physiological, radiographic, and biological		
	biomarkers to study the anti-fibrotic effect of pirfenidone in		
	CLAD post lung-transplantation		
Coordinating investigator:	[name]., M.S.		
Trial site:	University of Michigan		
Clinical phase:	Phase II		
Objective:	To evaluate the efficacy and safety of pirfenidone 801 mg TID		
	over 24 weeks in lung transplant recipients with chronic lung		
	allograft dysfunction		
Methodology:	Single centre, placebo-controlled, randomized, double-blinded,		
	clinical trial comparing safety and efficacy of Pirfenidone 801		
	mg TID to placebo over 24 weeks in patients with chronic lung		
	allograft dysfunction (CLAD)		
Number of patients	60 (30 per group)		
Treatments:	pirfenidone: 2403 mg daily		
	placebo: 2403 mg daily		
Diagnosis:	Spirometric and clinical diagnosis of CLAD		
Main inclusion criteria:	- Patients > 6 months after lung transplantation with		
	documented baseline values of FEV ₁ and FVC (mean of		
	two highest value measured 3 weeks apart)		
	- Baseline FEV ₁ and FVC > 50% predicted (to assure viable		
	graft)		
	- Diagnosis of CLAD (two consecutive spirometric values with		
	FEV_1 alone or both FEV_1 and $FVC < 80\%$ of baseline)		
Endpoints/Outcomes:	Primary:		
	- Change in functional small airways disease (fSAD) as		
	measured by parametric response mapping (PRM) at 24		
	weeks by treatment arm		
	Secondary:		
	- Change in FEV ₁ over 24 weeks by treatment arm		
	- Change in FVC over 24 weeks by treatment arm		
	- Number of subjects with treatment intolerance		
	- Number of subjects with adverse events related to		
	treatment with Pirfenidone		
	Exploratory:		
	- Change in bronchoalveolar lavage (BAL) mesenchymal		
	colony forming units (CFUs) by treatment arm		
	- Change in fibrotic phenotype of BAL mesenchymal cells		
	(expression of collagen, alpha smooth muscle actin, beta-		
	catenin, fibronectin) by treatment arm		
Safety criteria:	 Vital signs, physical examination 		
	- Clinical laboratory tests (hepatic function tests, creatinine)		
	- Reporting of adverse events		

Statistical Methods:	We will describe the distribution of fSAD change within and between treatment groups (n=30 per group) over a 6-month period. Preliminary data suggests that without treatment, fSAD increases 9% on average over a 6-month time period with SD of 9%. If pirfenidone halves this increase over 6 months, we would have a confidence interval for the treatment effect of 4.5+/-4.64%. Power to detect 6-month treatment differences is sensitive to assumptions of the standard deviation above and the ability of pirfenidone to reduce 6-month fSAD progression; a power analysis table is given below for various effect sizes and standard deviations that might be seen in the trial based on a sample size of 60 (30 per group). % Increase in FSAD for Pirfenidone				
		Group (vs 99	% FSAD incre	ase in	
		Placebo Gro	oup)		
	Std Dev	0%	2%	4.5%	
	5	>99%	>99%	93%	
	7	>99%	97%	69%	
	9	97%	84%	48%	
	 We will similarly summarize changes in spirometric particular and MSC CFU and phenotype over time between and groups. We do not anticipate any significant drop out because short duration of the study and this specific patient po who receive their clinical care at a specialized lung tracenter with no loss to follow up. 			rometric param etween and wit ut because of t patient popula zed lung transp	heters hin the ation blant

TABLE OF CONTENTS

Title Page	1
Clinical Trial Protocol Synopsis	2
Table Of Contents	4
Abbreviations	5
1. Specific Aims	6
2. Background/Rationale/Preliminary Studies	7
3. Investigator's Experience In Subject Area	9
4. Experimental Design	10
4.1 Endpoints	10
4.2 Study Design	10
4.3 Inclusion Criteria	10
4.4 Exclusion Criteria	10

11.3 Procedures For Eliciting, Recording And Reporting Adverse Events	
	23
11.4 Data Safety Officer	29
12. Study Closeout	29
13. References	30

DEFINITIONS AND ABBREVIATIONS

AE ALT AP	Adverse event Alanine aminotransferase Alkaline phosphatase
AR	Acute rejection
ATG	Antithymocyte Globulin
AST	Aspartate aminotransferase
BAL	Bronchoalveolar lavage
BOS	Bronchiolitis obliterans syndrome
CFU	Colony forming units
CLAD	Chronic lung allograft dysfunction
COPD	Chronic obstructive pulmonary disease
DSMB	Data Safety Monitoring Board
ECP	Extracorporeal photopheresis
EKG	Electrocardiogram
EOS	End of study
EOT	End of treatment
FEV1	Forced expiratory volume in 1 second
fSAD	Functional small airways disease
FVC	Forced vital capacity
HRCT	High resolution computed tomography
IMP	Investigational Medicinal Product
IPF	Idiopathic pulmonary fibrosis
IRB	Institutional review board
LFT	Liver function test
MSC	Mesenchymal stromal cells
OTIS	Organ Transplant Information System
NIH	National Institutes of Health
PFT	Pulmonary Function Tests
PI	Principal investigator
PRM	Parametric response mapping
RAS	Restrictive allograft syndrome
ULN	Upper limit of normal
UM	University of Michigan

1. SPECIFIC AIMS

- **Aim 1.** To determine if pirfenidone compared to placebo will stabilize progression of functional small airways disease (fSAD) as measured by parametric response mapping (PRM), a novel CT-based biomarker.
- **Aim 2.** To determine if pirfenidone therapy will stabilize pulmonary function as measured by FEV₁ and FVC in lung transplant recipients with chronic lung allograft dysfunction (CLAD).
- **Aim 3.** To investigate if pirfenidone therapy affects the fibrotic phenotype of mesenchymal cells collected from bronchoalveolar lavage (BAL).

2. BACKGROUND/RATIONALE/PRELIMINARY STUDIES

Our principle hypothesis is that pirfenidone therapy will stabilize lung function decline and slow progression of fSAD in lung transplant recipients with CLAD.

Greater than 50% of lung transplant recipients show signs of CLAD by 5 years posttransplantation (1). This process arises from development of graft fibrosis in a peri-bronchial (bronchiolitis obliterans or BO), peri-vascular, or fulminant interstitial and airway luminal fibrosis distribution (2, 3). Therapies to prevent or slow CLAD are lacking. Anti-fibrotic therapies may offer an avenue to prevent progression of CLAD and prolong allograft survival.

Pirfenidone, an oral anti-fibrotic agent, was approved for treatment of idiopathic pulmonary fibrosis (IPF) in 2014. In large multi-center, international clinical trials, pirfenidone has been shown to reduce the rate of FVC decline in patients with IPF with a favorable safety and tolerability profile (4, 5).

Small airways, the predominant histologic target of fibrotic remodeling in a chronically rejecting lung allograft, have been termed the "silent zone" of the lung secondary to difficulty in evaluating this disease process by pathology or imaging (6). While high resolution CT (HRCT) scans are routinely obtained at CLAD onset, HRCT findings in CLAD lack specific diagnostic features, and small airways cannot be visualized or evaluated by standard methods.

A novel imaging technology to evaluate functional small airways disease (fSAD) has been developed and validated at the University of Michigan. This technology, termed parametric response mapping (PRM), utilizes voxel by voxel comparison of inspiratory and expiratory HRCT images through co-registration to provide quantitative measures of fSAD. This tool has been utilized in patients with a variety of lung diseases including patients with chronic obstructive pulmonary disease (COPD) and lung transplant recipients (7-9). Higher levels of fSAD in lung transplant recipients with CLAD has been associated with decreased survival, and fSAD values have been shown to increase over time compared to transplant patients without chronic rejection (8, 9). We propose to utilize this novel imaging biomarker to track the change in fSAD, as it relates to change in traditional measures of FEV₁ or FVC, in patients with CLAD enrolled in this clinical trial. We have significant experience in longitudinal monitoring of lung function and have been pioneers in describing the natural history of spirometric decline after CLAD onset (10). Imbio Platform systems, a commercial company with quantitative image biomarker algorithms, will be utilized in this study.

Furthermore, this study will employ a novel biological biomarker of fibroproliferation, mesenchymal stromal cells (MSCs), in assessing the effect of pirfenidone on CLAD. Use of this biomarker is based on 10 years of work in our lab demonstrating that MSCs can be isolated from BAL of lung transplant recipients and are biomarkers of BOS (11, 12). The number of MSCs can be quantitated by a colony forming assay and now as a nested PCR based mRNA measure of unique lung-MSC transcription factors Foxf1 (11). The third aim of this study will investigate the effect of pirfenidone on MSC number and phenotype. This will be the first study analyzing novel imaging and MSC biologic markers of fibroproliferation following administration of a therapeutic agent for CLAD.

Schematic of Study Design

Prior to Enrollment

Obtain informed consent. Screen potential subjects by inclusion and exclusion criteria; obtain medical history; HCRT, BAL (optional), vital signs, EKG, spirometry, pregnancy test (if applicable), concomitant medications, Adverse events from time of signing consent.

4. EXPERIMENTAL DESIGN

4.1 ENDPOINTS

Primary:

- Change in functional small airways disease (fSAD) as measured by parametric response mapping (PRM) at 24 weeks by treatment arm

Secondary:

- Change in FEV₁ over 24 weeks by treatment arm
- Change in FVC over 24 weeks by treatment arm
- Number of subjects with treatment intolerance over 24 weeks
- Number of subjects with adverse events related to treatment with Pirfenidone

Exploratory:

- Change in bronchoalveolar lavage (BAL) mesenchymal colony forming units (CFUs) by treatment arm
- Change in fibrotic phenotype of BAL mesenchymal cells (expression of collagen, alpha smooth muscle actin, beta-catenin, fibronectin) by treatment arm

4.2 STUDY DESIGN

Single center, randomized, double-blind placebo controlled clinical trial of pirfenidone for the attenuation of progression of fSAD in lung transplant recipients with CLAD. A total of 60 patients will be enrolled in the trial.

Eligible patients will be randomized 1:1 to receive either pirfenidone 801 mg TID or placebo.

4.3 INCLUSION CRITERIA

- Lung transplant recipients 18 years of age or older.
- Greater than 6 months after single or bilateral lung transplantation
- Baseline FEV₁ and FVC values (mean of two highest value measured 3 weeks apart) > 50% predicted (to assure viable graft)
- Diagnosis of CLAD (two consecutive spirometric values of FEV₁ alone or both FEV₁ and FVC < 80% of baseline)

4.4 EXCLUSION CRITERIA

- Acute Rejection (AR) diagnosis by biopsy in the 28 days prior to enrollment
- Treatment with pulse steroids, Anti-thymocyte Globulin (ATG), extracorporeal photopheresis (ECP), plasmapheresis, or Immunoglobulin therapy aimed at CLAD within the 28 days prior to enrollment
- If the subject is receiving chronic Azithromycin therapy, the dose must be stable for the 28 days prior to enrollment
- Presence of active pulmonary infection at the time of enrollment as determined by an investigator in consultation with the treating pulmonologist
- Diagnosis of bronchial stenosis either a) requiring stenting, or b) thought to be responsible for the spirometric decline by principal investigator
- Abnormal liver function tests (AST or ALT > 2 x upper limit of normal (ULN), Alkaline phosphatase > 2.5 x ULN, total bilirubin > ULN) or known cirrhosis (>2 times upper limit of normal of AST/ALT/AP)
- Total WBC < 3.0 K/uL
- Moderate to Severe Renal insufficiency (CrCl <15 mL/min calculated by the Cockcroft-Gault equation)

- Use of any medication known to cause significant interactions with pirfenidone (strong CYP1A2 inhibitors such as Fluvoxamine or Enoxacin or inducers)
- Pregnancy or lactation. Women of child-bearing potential will have a pregnancy test at enrollment and must agree to maintain highly effective contraception with two methods of birth control from the date of consent through the end of the study.
- Tobacco use within 6 months
- History of alcohol abuse in the past 1 year as determined by the treating pulmonologist
- Any condition other than CLAD that will likely result in death in the next 1 year
- Any condition in the judgement of the principal investigator that would preclude participation in this study
- EKG with QTc interval > 500 msec at screening
- Listed for repeat lung transplantation

Excluded therapies:

The following therapies are not permitted during the study:

- Investigational therapy, enrollment in another therapeutic clinical trial within 30 days or 5 half-lives of study medication (whichever is longer)
- Fluvoxamine

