5.0 STUDY VISITS

5.1 Screening

Lung transplant recipients at the University of Michigan will be screened by the study team for participation in this trial. If deemed eligible, subjects will be approached regarding study, and the consent form as well as inclusion and exclusion criteria will be reviewed.

Screening Visit (Performed up to 6 weeks prior to baseline visit and initial study drug dosing) The following procedures will be completed at screening:

- Obtain and document informed consent
- Obtain sex, race, ethnicity, date of birth
- Vital signs (height, weight, temperature, blood pressure, heart rate, respiratory rate, pulse oximetry)
- Review medical history, including transplant history
- Review current medications
- Date of spirometric decline (defined as date of first spirometric measurement used to document spirometric decline) and CLAD phenotype
- Review of bronchoscopy results (if performed in the 6 weeks prior to screening visit)
- Blood draw for screening labs
 - AST, ALT, AP, total bilirubin, creatinine

Screening Bronchoscopy

Bronchoscopy is often employed in routine clinical care to evaluate decline in lung function in lung transplant patients. The University of Michigan (UM) has a standing Institutional Review Board (IRB) approved protocol that that allows for use of BAL fluid for research purposes. If clinical bronchoscopy has been performed within 6 weeks of screening, and no clinical indications of new infection are present (as determined by the principal investigator in consult with the treating pulmonologist), we will utilize the MSC results for this study. If bronchoscopy has not been performed, it may be done following screening and before enrollment, as an

optional part of this study. The informed consent document includes opt in/opt out language for bronchoscopy.

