5.2 Baseline Assessment (Visit 1, Week 0)

At the time of baseline, the coordinator will document the following:

- Vital signs (weight, temperature, blood pressure, heart rate, respiratory rate, pulse oximetry)
- Physical exam including general appearance, HEENT, cardiovascular, pulmonary, abdominal, neurologic, dermatologic, and musculoskeletal exams
- Current medications
- Safety blood work for renal and liver evaluation
 - AST, ALT, AP, total bilirubin, creatinine
- Review bronchoscopy results (if performed)
- ECG
- Perform spirometry
- Undergo an HRCT scan with inspiratory and expiratory image acquisition (if HRCT was not done in preceding 6 weeks)
- Serum pregnancy test (if applicable)
- Review adverse events

5.3 Visits 2, 3, 5, 6 (Weeks 4, 8, 16, 20): may be performed at study center or by local lab draw in conjunction with phone visit

- Safety labs to monitor renal and liver function AP, ALT, AST, total bilirubin, creatinine
- Review hospitalizations
- Review medication compliance
- Review concomitant medications
- Review adverse events

5.4 Visit 4 (Week 12):

- Vital Signs (weight, temperature, blood pressure, heart rate, respiratory rate, pulse oximetry)
- Physical exam including general appearance, HEENT, cardiovascular, pulmonary, abdominal, neurologic, dermatologic, and musculoskeletal exams
- Safety blood work for renal and liver evaluation
 - o AP, ALT, AST, total bilirubin, creatinine
- Spirometry
- ECG
- Review hospitalizations
- Review medication adherence
- Review concomitant medications
- Review adverse events
- 5.5 Visit 7 (Week 24):
 - Vital Signs (weight, temperature, blood pressure, heart rate, respiratory rate, pulse oximetry)
 - Physical exam including general appearance, HEENT, cardiovascular, pulmonary, abdominal, neurologic, dermatologic, and musculoskeletal exams Safety blood work for renal and liver evaluation

- o AP, ALT, AST, total bilirubin, creatinine
- Spirometry
- ECG
- HRCT scan
- Review hospitalizations
- Review medication adherence
- Review concomitant medications
- Review adverse events
- Collect unused study medication and return to investigational pharmacy
- Bronchoscopy with consent of patient and primary physician if no contraindication identified

5.6 Visit 8 (Week 28) (Phone visit):

At the 28 week phone visit, the coordinator will:

- Review hospitalizations
- Review adverse events
- Collect vital status

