C Week 28 visit may be performed as a telephone visit

D In women of child-bearing potential

E Immunosuppression drug levels will be collected and managed per standard of care

F LFTs will be monitored monthly

G HRCT may be done between screening visit and enrollment (visit 1)

H Results of BAL, if performed per standard of care, will be utilized as baseline if performed within the 6 weeks prior to baseline visit. Other bronchoscopies are optional.

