8. DRUG DOSAGE & ADMINISTRATION

Dosage and Administration

	Pirfenidone	Placebo
Substance	Pirfenidone	-
Pharmaceutical formulation	Capsule	Capsule
Source	Genentech	Genentech
Unit strength	267 mg	267 mg
Route	Oral	Oral
Dosage		
Days 1 through 7	267 mg three times daily	267 mg three times daily
Days 8 through14	534 mg three times daily	534 mg three times daily
Days 15 onward	801 mg three times daily	801 mg three times daily

- Take with food.
- Upon initiation of treatment, titrate to the full dosage of 2403 mg/day over a 14-day period as above.

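### The enzyme threshold attached to known cirrhosis in section 4.4 lets documented cirrhosis with low enzymes and normal bilirubin pass the liver exclusion if read literally (minor wording correction)

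*Combined protocol and SAP*

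**What the plan says.** Section 4.4 of the combined protocol and SAP puts the liver exclusion in one bullet with two parts.

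- **Laboratory limits:** AST or ALT above 2 x ULN, then "Alkaline phosphatase > 2.5 x ULN, total bilirubin > ULN".
- **Cirrhosis:** joined by an *or*, "known cirrhosis (>2 times upper limit of normal of AST/ALT/AP").

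No other section defines cirrhosis or names it as a reason for exclusion. The nearest general criterion is discretionary: "Any condition in the judgement of the principal investigator that would preclude participation in this study". Section 4.4 also excludes recent alcohol abuse and non-CLAD conditions likely to cause death within a year.

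At screening the team will "Review medical history, including transplant history" (section 5.1). Liver tests are drawn at screening and at baseline. During treatment, section 5.3 schedules "Safety labs to monitor renal and liver function AP, ALT, AST, total bilirubin, creatinine" at weeks 4, 8, 16 and 20, and sections 5.4 and 5.5 add weeks 12 and 24. Footnote F of Table 1 says "LFTs will be monitored monthly". The full dose applies from "Days 15 onward" (section 8).

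**The concern.** The bullet offers known cirrhosis as an alternative to the laboratory limits, so the clause should catch patients whose laboratory values pass. The parenthesis then ties cirrhosis to an enzyme threshold that nearly repeats those limits. Taken at its word, the clause has almost no function, and the patient it should add, one with documented cirrhosis but unremarkable enzymes, is left eligible.

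The bullet also carries two AP figures: 2.5 x ULN in the laboratory limits and 2 x ULN in the parenthesis. If the parenthesis defines cirrhosis, and any one raised enzyme is enough, an AP above 2 x ULN would exclude by itself and override the 2.5 x ULN limit.

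The stake is eligibility and safety. Section 8.1 lists liver problems among the common reactions to pirfenidone (at least 10%) and describes elevations of ALT, AST and bilirubin. Section 10.3 measures treatment intolerance by liver test elevations that lead to dose reduction or discontinuation. The hepatic entry rule should therefore have one meaning.

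**Working it through.** The plan states no figure on this point, so the check is of the rule itself.

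**Inputs, all from section 4.4.** AST or ALT > 2 x ULN excludes. AP > 2.5 x ULN excludes. Bilirubin > ULN excludes. The parenthesis sets > 2 x ULN for AST/ALT/AP.

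**Profiles.** For a patient with known cirrhosis, the cut-offs give:

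- AST/ALT: at or below 2, or above 2 x ULN (2 levels)
- AP: at or below 2, above 2 to 2.5, or above 2.5 x ULN (3 levels)
- bilirubin: at or below ULN, or above ULN (2 levels)

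That is 2 x 3 x 2 = 12 profiles.

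**Laboratory limits alone.** To pass, a patient needs AST/ALT at or below 2 x ULN (1 level), AP at or below 2.5 x ULN (2 levels) and bilirubin at or below ULN (1 level): 1 x 2 x 1 = 2 profiles pass, and 12 - 2 = 10 are excluded.

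**Effect of the cirrhosis clause on those 2 profiles**

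| Reading | Further profiles excluded | Profiles admitted |
|---|---|---|
| Literal, any one enzyme > 2 x ULN | 1 (AP above 2 to 2.5 x ULN) | 1 (all enzymes at or below 2 x ULN) |
| Literal, all three enzymes > 2 x ULN | 0 | 2 |
| Parenthesis deleted | 2 | 0 |

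The all-three reading adds nothing because both remaining profiles have AST and ALT at or below 2 x ULN. For a patient with documented cirrhosis, the definition and added-condition readings give the same result.

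**Cross-check on a finer grid.** AST, ALT and AP each took 7 values from 0.8 to 2.6 x ULN, and bilirubin took 3 values from 0.8 to 1.1 x ULN: 7 x 7 x 7 x 3 = 1,029 combinations. Under the literal any-one reading, 128 escape (4 x 4 x 4 x 2, the values at or below 2 x ULN for each enzyme and at or below ULN for bilirubin). The clause adds 64 exclusions to the laboratory limits (4 x 4 x 2 x 2), all with AP above 2 and up to 2.5 x ULN. Under the all-three reading it adds 0. With the parenthesis deleted, 0 escape.

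**When monitoring could first act.** Full dose starts on day 15, after 14 days of titration. Taking week 4 as day 28 with the +/- 7 day window in Table 1, and assuming no titration delay, the first on-treatment test follows 28 - 14 = 14 days at full dose (range 21 - 14 = 7 to 35 - 14 = 21). There are 6 scheduled on-treatment tests: weeks 4, 8, 12, 16, 20 and 24.

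**The case against.** The strongest reply is that this is loose drafting and not a real gap. A sensible investigator would see that known cirrhosis is meant to exclude, since no other reading gives the phrase a purpose. Parentheses in the criteria are not always operative: in section 4.3, "> 50% predicted (to assure viable graft") gives a reason and not a rule. That is fair, and it is why the point is minor. But other parentheses do carry the rule, such as the spirometric definition of CLAD in section 4.3 and the creatinine clearance limit in section 4.4, so a screener could treat this one the same way.

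A second reply is that other safeguards would catch such a patient. There are several: history review, baseline physical examination, two rounds of liver tests before dosing, the alcohol and prognosis criteria, and investigator judgement. On treatment, section 8.1 calls for close monitoring, with possible dose reduction or interruption, at AST/ALT of 3 to 5 x ULN. It requires permanent discontinuation above 5 x ULN, or at lower levels with symptoms or bilirubin above 2 x ULN. The Safety Officer reviews adverse event and laboratory data. These limit the risk without closing the gap. Repeat liver tests do not identify a patient whose enzymes are low, investigator judgement is discretionary, and the on-treatment measures act only after exposure.

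Two objections stand in full. The documents do not show that cirrhosis with low enzymes carries excess risk here. The override of the 2.5 x ULN AP limit arises only if any one enzyme suffices. It is also possible that the sponsor meant to exclude only cirrhosis with raised enzymes, so the clinical team should confirm the intent.

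**Conclusion.** The concern holds as a minor wording correction. Read literally, the bullet does not exclude documented cirrhosis with AST, ALT and AP at or below 2 x ULN and bilirubin at or below ULN: 1 of 12 profiles is admitted, or 2 of 12 if all three enzymes must be raised, against 0 of 12 without the parenthesis. The counts describe the rule; they say nothing about how often such patients occur or how they would fare.

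The conclusion rests on taking the parenthesis as a definition or an added condition. The judgement that it departs from intent rests on the clause having no real function otherwise. Sample size, power and the primary analysis are unaffected.

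**What to change.** Delete the parenthesis and state two separate criteria in section 4.4:

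- (a) AST or ALT > 2 x ULN, alkaline phosphatase > 2.5 x ULN, or total bilirubin > ULN;
- (b) known cirrhosis, regardless of enzyme levels.

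Before finalising, the clinical team should confirm that any known cirrhosis is meant to exclude and that 2.5 x ULN is the single AP limit. If 2 x ULN was intended for AP, it belongs in (a). The cost is one eligibility wording change, with no added test, visit or patient.
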